8.4 Prior and concurrent therapy

Any prior, concurrent, or procedural medications or therapy given to or taken by the subject within 21 days before and up to the time of PET imaging will be recorded in the CRF along with the indication. Either the generic or the trade name may be recorded.

8.5 Treatment compliance

Subjects will receive radiotracers under direct supervision of qualified study personnel. Each administration volume and total amount of radioactivity injected will be checked, and the details—including date and time of injection—will be recorded.

9 TREATMENT PERIOD

Informed consent will be obtained. All subjects must satisfy one inclusion criterion and none of the exclusion criteria listed. Signed and dated informed consent must be obtained from all subjects before any study-specific procedures are performed. The consent document may be sent to a potential participant prior to obtaining consent for their information. A screening visit will be performed within 2 months before radiotracer administrations, however can be performed on the day of PET/CT imaging. Subjects will be permitted to continue taking any routine or necessary medication.

The following data will be collected on study-specific CRFs.

- Date of birth
- Weight
- Height
- Concurrent medications
- Medical history and concurrent diseases
- Report and date of most recent histological tissue evaluation from any known prostate cancer
- Results of screening tests

Personal data (including contact information) will be collected with the subject's permission and only to the extent that is necessary for the purposes of the study.

Vital signs (pulse, respirations, systolic and diastolic blood pressure) are recorded. A cannula (or indwelling catheter) will be placed into a vein, preferably in the antecubital region, for tracer administration.

The injection site will be examined for any abnormal findings before dosing. In the interests of comfort, subjects will be advised to empty their bladder and, if necessary, complete a bowel movement before being positioned on the scanner table.

9.1 ⁶⁸Ga-PSMA PET/CT

a) ⁶⁸Ga-PSMA-11 PET preparation and injection:

The injected dose will be 111-259 MBq (3-7 mCi) of ⁶⁸Ga-PSMA-11 PET. PET imaging will begin 50-100 minutes after injection. Scan time per bed position will be determined based on expected count statistics related to the administered dose.

b) Patient preparation: no fasting is required.

c) PET protocol: Scan coverage will extend from mid-thigh to the base of the skull, starting from the mid-thighs to prevent urinary bladder radiotracer accumulation at the start of PET imaging. Scan time per bed position will be determined based on expected count statistics, which is determined mainly by the administered dose. Scan time will therefore be between 15 and 40 minutes. In certain circumstances, coverage may be extended to the toes. Contrast may be administered as needed.

d) Patient monitoring: Vital signs will be assessed immediately before and after injection of ⁶⁸Ga-PSMA-11 (HR and supine BP). Patients will be monitored for adverse events during injection and for two hours

after radiotracer administration. Additionally, patient's vitals (HR and supine BP) will be checked at the completion of the imaging study prior to leaving the imaging center.

- e) Patient follow-up: Patients will be contacted by phone one to three days after ⁶⁸Ga-PSMA-11 PET to assess for the development of delayed adverse events. Patients will be seen in the clinic if there are any concerning study related adverse events requiring further evaluation.

9.2 Post-Treatment Period

We will adhere to the follow-up procedures specified in IND #133858. Patients are encouraged to self-report any possible side effect to the study team.

9.2.1 Target identification

In-vivo imaging (PET and/or MRI) will be reviewed by participating investigators for intraprostatic lesions suspicious for significant prostate cancer. After registration of imaging data to the T2-weighted MRI, the responsible radiologists ([name] and [name], or designees) will determine potential target areas for image-guided (targeted) prostate biopsy within the T2-weighted MRI (reference space). Candidate targets are the known PI-RADS 3-5 lesions, where higher PI-RADS scores will be preferentially selected. Any PI-RADS 5 lesion will be targeted for biopsy (unless there are more than 3). ⁶⁸Ga-PSMA positive lesions not identified by mpMRI as PI-RADS 3-5 will be considered as well. Currently available preliminary retrospective data suggest that a suitable threshold for ⁶⁸Ga-PSMA positivity (defining significant disease) would be ≥ 2 standard deviations above prostate background.³²

To limit the burden to the subject, no more than 3 target locations will be selected for biopsy. If more than 3 targets are present (from both PET and/or MRI), the most suspicious 3 are selected; in case of a tie, the largest will be selected. The selected targets are then transferred to the navigated ultrasound workstation used for targeted prostate biopsies.

Radiomics analysis results will not be used to identify targets for prostate biopsies.

9.2.2 Prostate biopsy procedure

Prostate cancer subjects recruited for this study are expected to receive tissue sampling for clinical (diagnostic) purposes. Accordingly, all subjects already had a prior mpMRI indicating presence of a prostate lesion potentially representing prostate cancer (PI-RADS 3-5).

Targeted (fusion) prostate biopsies based on TRUS-MRI guidance are routine clinical practice at Michigan Medicine. While typically all biopsy targets are sampled, it is at the discretion of the physician performing the prostate biopsy which of the selected targets are biopsied. Typically, a total of 2 sample cores are obtained from each target. However, to account for biopsy cores missing the target area the exact number of biopsy cores obtained from a given target is at the discretion of the physician performing the prostate biopsy procedure.

The histological results of the biopsy will be compared to PI-RADS scores and respective visual and quantitative radiotracer uptake measures.

Patient monitoring after the prostate biopsy procedure will be done according to standard of care. The patient will receive specific instructions and guidance for minor and more serious adverse effects.

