5 STUDY OBJECTIVES AND PURPOSE

The primary study aim is the prospective comparison of standard-of-care mpMRI vs. combined ⁶⁸Ga-PSMA PET and mpMRI (⁶⁸Ga-PSMA fusion PET/MRI) for the detection and risk-stratification of clinically significant primary PCa.

Following (clinical) mpMRI and (research) ⁶⁸Ga-PSMA PET/CT imaging, we will perform targeted and standard 12-sample prostate biopsies. Biopsy targets will be defined from mpMRI and ⁶⁸Ga-PSMA PET; mpMRI interpretation will be done in accordance with PI-RADS v2.

Primary objective: We will determine the sensitivity and specificity of mpMRI alone and mpMRI in combination with ⁶⁸Ga-PSMA PET (i.e., fusion PET/MRI) for the detection of primary Gleason $\geq 3+4$ PCa. Primary outcome measure: determination whether the positive likelihood ratio (LR) for ⁶⁸Ga-PSMA PET-MRI is at least 1.28 greater than that of standard-of-care mpMRI. Reference standard will be pathology defined as targeted plus standard prostate biopsy, and prostatectomy, when available.

Secondary objective: We will determine the safety of ⁶⁸Ga-PSMA. We will also determine frequency and location of ⁶⁸Ga-PSMA positive lesions, such as potential extra-prostatic extension, lympho-nodal and/or distant metastatic disease positive on ⁶⁸Ga-PSMA but not identified by conventional (standard) imaging. While histological verification would be desirable, the decision for or against tissue verification will depend on clinical decisions making only, and not be required due to study participation.

Exploratory objective: We will evaluate whether radiomics classifiers (obtained from mpMRI and ⁶⁸Ga-PSMA identified targets) could improve identification and risk stratification of significant PCa. Reference standard will be pathology defined as targeted plus standard prostate biopsy, and prostatectomy, when available.

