8.3 Blinding

This will be an open-label study and no blinding will be performed.

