12.5.2 Analysis of Primary Endpoints

PET images will initially be interpreted by a board certified nuclear medicine physician or a board-certified radiologist experienced in reading PET at the time of the imaging study at Michigan Medicine. Upon request, case report forms and coded ⁶⁸Ga-PSMA PET/CT imaging data will be provided to the FDA for review.

Intraprostatic lesions identified by mpMRI as PI-RADS 3-5 will be graded visually on a two-point scale as either positive or negative for elevated ⁶⁸Ga-PSMA uptake relative to prostatic gland uptake (0=Negative or 1=Positive).

Any focal intraprostatic elevated ⁶⁸Ga-PSMA uptake relative to prostatic gland that was not identified by mpMRI (as PI-RADS 3-5) but was targeted at biopsy will also be evaluated visually as either positive or negative (0=Negative or 1= Positive).

All subjects with histopathology correlates will be analyzed for the primary aim. Sensitivity and specificity, positive and negative predictive values, and accuracy (along with the corresponding two-sided 95% confidence intervals) will be determined on a per-subject and per-lesion basis for ⁶⁸Ga-PSMA-11 PET and mpMRI regarding the detection of Gleason \geq 3+4 cancer. Standard reference of truth is histopathology from all individual biopsy cores, targeted and standard cores.

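### PET status may influence how many cores a target receives; with all cores as truth, a PET used to down-classify mpMRI lesions could then show a spurious gain in positive LR

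*Combined protocol and SAP*

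**What the plan says.** All references are to the combined protocol and SAP.

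- Section 8.3: "This will be an open-label study and no blinding will be performed".
- Section 9.2.1: targets come from PET and mpMRI together, and "no more than 3 target locations will be selected for biopsy". Then: "The selected targets are then transferred to the navigated ultrasound workstation used for targeted prostate biopsies". The section does not say whether PET status travels with them.
- Section 9.2.2: the usual practice is to sample every target, but "it is at the discretion of the physician performing the prostate biopsy which of the selected targets are biopsied". On intensity: "Typically, a total of 2 sample cores are obtained from each target"; however, "the exact number of biopsy cores obtained from a given target is at the discretion of the physician performing the prostate biopsy procedure". The reason given for that latitude is that cores can miss the target.
- Section 5: "we will perform targeted and standard 12-sample prostate biopsies".
- Section 9.2.5: the workstation records the position of every core, standard or targeted.
- Section 12.5.2: "Standard reference of truth is histopathology from all individual biopsy cores, targeted and standard cores".
- Section 12, primary objective: a mixed-effects logistic model tests the PET coefficient, and positive LR is compared between mpMRI alone and mpMRI plus PET.

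No section masks the operator to PET, sets a minimum or equal core count, adjusts for the number of cores, or says how a selected but unsampled target is handled.

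**The concern.** The index test can affect how hard its own reference standard is sought. Section 9.2.2 accepts that a core may miss, so a target with more cores has a higher chance of yielding Gleason 3+4 or above. If PET-positive targets receive more cores, cancers are found where PET is positive and missed where it is negative. The missed ones are scored as PET true negatives. An uninformative PET would then be associated with the histology label, which affects both the PET coefficient and, depending on how PET and mpMRI are combined, the LR+ comparison that carries the primary outcome. No planned analysis would reveal or correct this.

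**Working it through.** **Plan's figures.** Section 12.1 assumes mpMRI sensitivity and specificity of 0.789 each: LR+ = 0.789/0.211 = 3.74, which reproduces. The plan's target difference is 1.28 (5.02 − 3.74). The stated gains of +0.02 and +0.15 would give 0.809/0.061 = 13.26, not 5.02. That is a separate matter; 1.28 serves here only as a yardstick.

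**Inputs from the documents.** Prevalence of significant cancer is 48% in Table 1, which is per subject. The only lesion-level rate is 30/90 = 33%, from the prior choline trial (section 12).

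**Assumptions not in the documents.** PET is independent of disease and of PI-RADS, and is positive in half of targets. Detection per targeted core is c = 0.6. PET-positive targets get 4 cores and PET-negative targets 2. Standard cores find a target's cancer with probability s = 0 or 0.5.

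**Formulas.** With k cores, detection d = 1 − (1 − s)(1 − c)^k. With prevalence π, and d₊ and d₋ for PET-positive and PET-negative targets:

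- apparent sensitivity = d₊/(d₊ + d₋)
- apparent 1 − specificity = (1 − πd₊)/(2 − πd₊ − πd₋)
- apparent gain ≈ 3.74 × (LR+ of PET − 1)

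| c | π | s | d₊ / d₋ | Sens. | 1 − spec. | LR+ of PET | Gain |
|---|---|---|---|---|---|---|---|
| 0.6 | 0.48 | 0 | 0.974 / 0.840 | 0.537 | 0.471 | 1.14 | +0.52 |
| 0.6 | 0.48 | 0.5 | 0.987 / 0.920 | 0.518 | 0.485 | 1.07 | +0.25 |
| 0.6 | 0.33 | 0 | 0.974 / 0.840 | 0.537 | 0.484 | 1.11 | +0.41 |
| 0.6 | 0.33 | 0.5 | 0.987 / 0.920 | 0.518 | 0.492 | 1.05 | +0.20 |
| 0.9 | 0.48 | 0 | 1.000 / 0.990 | 0.502 | 0.498 | 1.01 | +0.04 |

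Gains use unrounded values. As shares of the yardstick, 0.52/1.28 = 41% and 0.20/1.28 = 16%.

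**Full tables under an AND rule** (PI-RADS ≥4 and PET-positive). Scaling 3.74 ignores that missed cancers also become mpMRI false positives. With d̄ the mean of d₊ and d₋:

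- mpMRI LR+ = 0.789(1 − πd̄)/[0.789π(1 − d̄) + 0.211(1 − π)]
- Combined sensitivity = 0.789d₊/(d₊ + d₋)
- Combined false-positive fraction = 0.5[0.789π(1 − d₊) + 0.211(1 − π)]/(1 − πd̄)

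First row of the table: mpMRI 0.4454/0.1449 = 3.07; combined 0.4237/0.1058 = 4.01; gain +0.93. Fourth row: 3.52 and 3.87; gain +0.35. The scaled figures are therefore on the low side under this rule.

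At 48% prevalence and 4 versus 2 cores, the full-table gains at c = 0.5, 0.7 and 0.9 are +1.13, +0.62 and +0.08 without standard cores, and +0.65, +0.32 and +0.04 with s = 0.5. None reaches 1.28. At 4 versus 1 cores without standard cores they are +2.66, +2.08 and +0.78. With equal cores the gain is 0.00 throughout.

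**OR rule** (PI-RADS ≥4 or PET-positive). At c = 0.7, π = 0.48, s = 0 and 4 versus 2 cores, mpMRI LR+ is 3.34 and combined LR+ is 1.46: the uninformative PET lowers LR+.

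**PET coefficient.** Simulation with 2,000 runs, 100 independent lesions, fixed-effects logistic regression and s = 0: false significance in PET's favour occurs in 17%, 8% and 3% of runs at c = 0.5, 0.7 and 0.9 (4 versus 2 cores), against a nominal 2.5%. With s = 0.5 it is 8%, 4% and 4%.

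**Skipped targets.** Suppose half of PET-negative targets are skipped and excluded, with equal cores otherwise. Under the AND rule, sensitivity is 0.789 × 0.5/0.75 = 0.526 and 1 − specificity is 0.211 × 0.5/0.75 = 0.141, so LR+ stays at 3.74.

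Now suppose 30% of PET-negative targets are unsampled and labelled from standard cores alone (s = 0.5), with two-core truth of 0.84 elsewhere. PET-negative detection is 0.7 × 0.84 + 0.3 × 0.5 = 0.738. At π = 0.48, sensitivity is 0.84/1.578 = 0.532, 1 − specificity is 0.5968/1.2426 = 0.480, LR+ of PET is 1.11 and the scaled gain is +0.41.

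**The case against.** The best defence is that section 9.2.2 describes two cores per target and sampling of all targets as usual, and gives missed cores, not PET status, as the reason for varying the number. Every subject also has 12 standard cores, which in these calculations roughly halve the effect at an assumed detection of 0.5. No document shows a 4-versus-2 imbalance, and at high per-core detection the effect vanishes. All of this stands and limits the size. It does not close the gap, because a usual practice is not a rule and nothing checks whether core numbers differ by PET status.

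Three stronger readings are tempting, and the documents do not support them.

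- A reader might infer that the freedom to choose which targets are biopsied itself inflates LR+. Skipping and excluding by PET status leaves LR+ unchanged under the AND rule. The bias needs unequal core numbers, or unsampled targets called negative on standard cores alone.
- A reader might infer that the operator sees PET status and samples accordingly. The plan only fails to prevent it.
- A reader might infer that the bias must favour PET/MRI. For LR+ that needs an AND-type rule. Section 11.2.3 expects modification of the mpMRI score to be the main effect, and section 12 projects mostly a specificity gain; both fit such a rule. But section 11.2.3 also allows PET to add lesions, and no rule is written down.

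The comparator matters too. The primary objective in section 12 names PI-RADS ≥3, whereas 0.789/0.789 is the site's figure for PI-RADS ≥4. Among PI-RADS 3–5 targets a ≥3 threshold has LR+ 1, and the uninformative PET then shows 1.20, 1.08 or 1.01 at c = 0.5, 0.7 or 0.9 (4 versus 2 cores, no standard cores).

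**Conclusion.** The concern holds as a possibility that the plan leaves open, not as a demonstrated bias. No blinding, operator control of core numbers and an all-cores reference standard together allow verification intensity to depend on PET status. If it does, and PET down-classifies mpMRI lesions, an uninformative PET can show a gain in LR+. By scaling 3.74, the central case runs from about +0.5 to about +0.2 (+0.93 to +0.35 with full tables), and it is near zero at 0.9 detection per core. Per-core detection, standard-core detection, the PET-positive share and the core imbalance are all assumptions. A spurious gain of 1.28 or more needs a marked imbalance, such as 4 versus 1 cores with per-core detection of 0.7 or less and no help from standard cores. Under an OR rule LR+ moves the other way. This is worth correcting because prevention is cheap, not because the primary result is shown to be unsound.

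**What to change.** - **Section 9.2.1:** transfer the selected targets to the workstation as numbered regions without a PET-status label. Acknowledge that PET-only targets may still be inferred, since they are absent from the PI-RADS report.
- **Section 9.2.2:** record the number and order of cores per target, and any selected target not sampled. Leave the operator's discretion unrestricted.
- **Section 12.5.2:** keep all cores as the primary reference standard and report cores per target by PET status. Prespecify two sensitivity analyses of LR+ and the PET coefficient: (a) targeted-core truth limited to the first two cores of each target, plus standard cores; (b) unsampled targets classified from standard cores crossing the registered region, as opposed to excluded.

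Neither sensitivity analysis should become primary. The first discards cancers already found in later cores, and the second can itself create the bias, as the +0.41 example shows.

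Cost: the operator does not see the PET label during sampling, though PET-derived targets remain on the workstation. There is also a little extra recording and analysis. No additional cores or staff are needed.

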9.2.3 Pathological Evaluation

The histological confirmation serves as standard of truth. All biopsy cores obtained, whether targeted or standard, will be assessed for diagnosis.

Routine histology of all prostate biopsy cores will be performed according to the established institutional guidelines. Biopsy samples will be processed for routine histological assessment (hematoxylin/eosin (HE) stain) using the paraffin embedding process and 3 μ m sections. Each tumor focus will be assigned a primary and secondary Gleason grade and staged according to recent American Joint Committee on Cancer (AJCC) guidelines. Some cuts may remain unstained for later immunohistochemistry (IHC) for PSMA and/or other additional PIN cocktail (cocktail of basal markers and AMACR) IHC, when deemed necessary for clinical purposes ⁵⁴.

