Primary objective: Mixed-effects logistic regression is used to evaluate the primary objective, the diagnostic performance of mpMRI and PET. The outcome is Gleason $\geq 3+4$ or not, and predictors are PI-RADS v.2 score and ^{68}Ga -PSMA PET uptake. We employ a mixed effects model to account for within-subject correlation among one or more biopsied lesions. We will test the null hypothesis that the regression coefficient of PET is equal to zero versus an alternative hypothesis that it is not equal to zero, assessing whether ^{68}Ga -PSMA PET is an important factor to identify aggressive PCa. We also compare predictive accuracies of (1) PI-RADS ≥ 3 only and (2) PI-RADS ≥ 3 plus ^{68}Ga -PSMA PET models by examining the confidence intervals of a predictive performance measure: positive likelihood ratio (positive LR).

Secondary objectives: We are not expecting any adverse events related to the administration of the radiotracer. However, frequency tables will be generated to display the safety profile of ^{68}Ga -PSMA (secondary objective).

We will also record the frequency and location of extra-prostatic ^{68}Ga -PSMA positive lesions (such as extra-prostatic extension, lympho-nodal and/or distant metastatic disease) not identified by conventional (standard) imaging. Formal statistical evaluation is not planned as the frequency of such findings is expected to be low.

Exploratory objective: We will evaluate whether radiomics classifiers (obtained from mpMRI and ^{68}Ga -PSMA identified targets) could improve identification and risk stratification of significant PCa. Reference standard will be pathology defined as targeted plus standard prostate biopsy, and prostatectomy, when available. The performance of the different classifiers in detecting significant PCa will be evaluated by using the area under the receiver-operating characteristic (ROC) curve (AUC) using pathology as gold standard.⁵⁷

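### The plan does not require Gleason grading, the truth for the primary endpoint, to be done without knowledge of PET status or target source

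*Combined protocol and SAP*

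**What the plan says.** Section 9.2.3 (Pathological Evaluation) gives histology its role: "The histological confirmation serves as standard of truth". On how it is done: "Routine histology of all prostate biopsy cores will be performed according to the established institutional guidelines", and "Each tumor focus will be assigned a primary and secondary Gleason grade". No masked, central or second reading is mentioned.

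Section 8.3 (Blinding) is the only statement on masking in the document: "This will be an open-label study and no blinding will be performed". It makes no exception for pathologists.

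Section 12.5.2 fixes the reference for the primary analysis: "Standard reference of truth is histopathology from all individual biopsy cores, targeted and standard cores". Section 12 sets the dichotomy: "The outcome is Gleason $\geq 3+4$ or not". Section 5 adds prostatectomy pathology to the reference when it is available.

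On timing, Section 12.5.2 has PET first interpreted by a physician "experienced in reading PET at the time of the imaging study at Michigan Medicine", that is, before biopsy. Sections 5, 9.2.1 and 9.2.5 have biopsy targets chosen from both mpMRI and PET, including PSMA-positive lesions that mpMRI did not score PI-RADS 3-5. Nothing in Sections 9.2.1 to 9.2.3 says what the specimen label or pathology request may show.

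**The concern.** The primary endpoint rests on one histological boundary, 3+3 against 3+4 or higher. If the person grading a borderline core knows that it came from a PSMA-avid target, the index test can influence the reference standard.

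Upgrading a core from a PET-positive target can turn a PET/MRI false positive into a true positive. If mpMRI had called the same man negative, the same decision turns an mpMRI true negative into a false negative. Both moves favour PET/MRI. The planned mixed-effects model takes the grade as given and would not correct this.

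This is separate from imaging readers knowing the pathology, and from the operator's discretion over how many cores to take. Here the grade itself could move.

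**Working it through.** **Plan's own figures.** LR+ = sensitivity/(1 − specificity). Section 12.1 assumes 0.789/0.789 for model (1): 0.789/0.211 = 3.74, which reproduces. The stated 5.02 for model (2) does not follow from the stated gains of 0.02 and 0.15 (0.809/0.061 = 13.26); it matches a specificity gain of 0.05 (0.809/0.161 = 5.02). That is a separate matter. Here 1.28 serves only as a yardstick.

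**Inputs.** Table 1 projects, per 100 men by maximum grade, 26 benign, 26 with 3+3 and 48 with 3+4 or higher, so 48 cases and 52 non-cases. The number of men regraded, k, is an assumption, because the documents give no rate of grade drift.

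**One-way upgrade.** Give both tests the same counts, so that PET adds nothing, and move k men who are PET/MRI positive and mpMRI negative from 3+3 to 3+4. With TP and FP at baseline:

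- PET/MRI LR+ = [(TP + k)/(48 + k)] / [(FP − k)/(52 − k)]
- mpMRI LR+ = [TP/(48 + k)] / [FP/(52 − k)]

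*Base A, 0.789/0.789:* TP = 38, FP = 11, LR+ = (38/48)/(11/52) = 3.74.

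*Base B, Table 1 at PI-RADS 4 or higher:* TP = 26 + 17 = 43; FP = (9 + 13) + (1 + 3) = 26; LR+ = (43/48)/(26/52) = 1.79.

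| k | Base A: PET/MRI vs mpMRI | Gap | Base B: PET/MRI vs mpMRI | Gap |
|---|---|---|---|---|
| 1 | 4.06 vs 3.60 | 0.46 | 1.83 vs 1.72 | 0.11 |
| 2 | 4.44 vs 3.45 | 0.99 | 1.88 vs 1.65 | 0.22 |
| 3 | 4.92 vs 3.32 | 1.60 | 1.92 vs 1.59 | 0.33 |

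With the minimum of 38 cases and 62 non-cases (30/38 and 13/62), the Base A gaps become 0.43, 0.90 and 1.43.

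**How many men could move.** At the PI-RADS 4 cut, the mpMRI-negative men are the PI-RADS 3 row of Table 1, which has 10 men with 3+3. If PET/MRI is falsely positive at 11/52 independently of mpMRI, 10 × 11/52 = 2.1 are eligible. The count depends on how the inputs are combined. On Base A's own mpMRI specificity it is 26 × 41/52 × 11/52 = 4.3. On Base B's false-positive rate it is 10 × 26/52 = 5, and regrading all five gives (48/53)/(21/47) − (43/53)/(26/47) = 2.03 − 1.47 = 0.56. Positive correlation between the tests lowers each count.

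**Drift in both directions, Base A rates.** Let a share f of PET/MRI-positive 3+3 men be upgraded and the same share of PET/MRI-negative men at 3+4 or higher be downgraded. For f = 10% and uncorrelated tests, 26 × 0.211 × 0.10 = 0.55 men go up and 48 × 0.211 × 0.10 = 1.01 go down.

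- PET/MRI: (38.42/47.54)/(10.42/52.46) = 4.07
- mpMRI: (37.19/47.54)/(11.66/52.46) = 3.52
- Gap: 0.55

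With within-class correlation of 0, 0.3 and 0.6, the gaps are 0.55, 0.40 and 0.23 at 10% (1.6 men regraded), 1.11, 0.83 and 0.50 at 20% (3.1 men), and 1.70, 1.30 and 0.82 at 30% (4.7 men). All favour PET/MRI.

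**When no gap arises.** If the upgraded men are positive on both tests at the PI-RADS 4 cut, both LR+ values rise equally from a common base. This is specific to that cut. Section 12 names PI-RADS 3 or higher for model (1), which every enrolled man meets under Section 7.2, so per-subject mpMRI LR+ stays at 1/1 = 1. On Base A, upgrades would then move only the PET/MRI value (3.74 to 4.06, 4.44 and 4.92).

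**Unit.** These are per-subject figures. Section 12 models lesions within subjects, and the documents give no lesion counts from which to compute a per-lesion figure.

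**The case against.** The strongest reply is that no section says PET status or target source reaches pathology. The no-blinding line is a general open-label statement placed among treatment procedures and does not mention pathologists, and grading to institutional guidelines limits drift. The first part stands: a reader might infer that grading is in fact unmasked, and the documents do not show this. They show only that masking is not required and that the single statement on the subject rules blinding out. Guidelines may reduce drift but are not masking.

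A reader might also conclude from Base A that three grade calls are enough to produce the whole 1.28. The documents do not support that as a general statement. It pairs Table 1's 48/52 split with an accuracy that Table 1 does not give. On Table 1's own counts three calls yield 0.33, about a quarter of 1.28, and about two eligible men are expected when Table 1's 10 men are taken at the 11/52 rate. On Base A, reaching 1.28 by upgrading alone requires regrading 53% to 84% of PET/MRI-positive 3+3 men in the correlation model.

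Nor would such a bias be beyond repair. Cores are paraffin-embedded under Section 9.2.3, so a masked re-read would be possible later, although none is planned.

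**Conclusion.** The concern holds as a gap in the design. The plan allows the reference standard to be graded with the index test known, and grade calls that follow PET would favour PET/MRI in the LR+ contrast. It is not shown that this will happen.

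The size is uncertain. With no true difference, one to three upgraded men give a spurious gap of 0.46 to 1.60 from the 0.789/0.789 base, or 0.11 to 0.33 from Table 1's counts at PI-RADS 4 or higher. These figures assume that the moved men are PET/MRI positive and mpMRI negative, of whom few are expected, and they are per subject. The direction is firmer than the magnitude. The case for acting rests mainly on how little prevention costs.

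**What to change.** In Section 9.2.3, and as a stated exception in Section 8.3, specify that:

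- targeted cores go to pathology under neutral target numbers;
- the request omits PET status and which modality chose the target;
- pathologists grade without consulting the PET report, since neutral labels alone do not prevent access to a report held at the same institution;
- the Gleason grade signed out on that basis is the one used for the primary endpoint;
- the study team holds the code linking target number to imaging source until sign-out.

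Apply the same rule to prostatectomy grades used as reference. Section 9.2.4 plans to register PET with the specimen, so the grade should be signed out before PET is shown.

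The cost is a labelling step and a few sentences of protocol text, with no added procedure or reading. The small downside is that the pathologist does not see the research PET information before sign-out.
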